10.1.6 Time to Progression

CONFIDENTIAL

This document is confidential. Do not disclose or use except as authorized.

Time to Progression: Time to Progression (TTP) is defined as the time from registration to progression, or censored at the date of last disease evaluation for those without progression reported.

#### 10.1.7 Response Review

Central review of the radiology assessments is planned using tumor metrics core at the DFCI.

### 10.2 Other Response Parameters

Descriptive statistics (including mean, standard deviation (SD), minimum, maximum, median, interquartile range) will be provided on levels of serum hormones and changes from baseline.

#### 10.2.1 SPECT/CT

In an imaging substudy, patients enrolled at DFCI only will undergo quantitative SPECT/CT as part of the standard of care bone scans at baseline, and at the time of the first two follow up bone scans. The field of view will be determined by the nuclear medicine physician depending on the location of the lesions on the planar images. The imaging parameters for SPECT/CT will follow DFCI institutional policies for SPECT/CT bone scanning. xSPECT Quant software will be used to determine activity concentration on quantitative SPECT/CT in target bone lesions before and after therapy. Descriptive statistics (including mean, standard deviation (SD), minimum, maximum, median, interquartile range) will be provided on activity concentration of 99mTc-MDP on quantitative SPECT/CT. The data collected from the imaging substudy is exploratory and not used as part of decision making for the response assessment.

CONFIDENTIAL

This document is confidential. Do not disclose or use except as authorized.

## 11. ADVERSE EVENT REPORTING REQUIREMENTS

### 11.1 Definitions

#### 11.1.1 Adverse Event (AE)

An AE is any undesirable sign, symptom or medical condition or experience that develops or worsens in severity after starting the first dose of study treatment or any procedure specified in the protocol, even if the event is not considered to be related to the study.

Abnormal laboratory values or diagnostic test results constitute AEs only if they induce clinical signs or symptoms or require treatment or further diagnostic tests.

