## 6. EXPECTED TOXICITIES AND DOSING DELAYS/DOSE MODIFICATIONS

The starting dose of enzalutamide will be 160 mg daily. In the presence of any enzalutamide related toxicities > grade 2 (NCI CTCAE version 4), during treatment with enzalutamide at the starting dose level, the dose of enzalutamide will be decreased to 120 mg daily in the subsequent dose level. Two levels of dose de-escalation are planned for the study. If > grade 2 toxicity occurs at dose level -2, participants will be removed from the protocol.

Dose Level	Enzalutamide
Starting dose level	160 mg orally once daily
-1	120 mg orally once daily
-2	80 mg orally once daily

Toxicity assessments will be done using the NCI Common Terminology Criteria for Adverse Events (CTCAE) (version 4) which is identified and located on the CTEP website at: [http://ctep.cancer.gov/protocolDevelopment/electronic\\_applications/ctc.htm](http://ctep.cancer.gov/protocolDevelopment/electronic_applications/ctc.htm).

If possible, symptoms should be managed symptomatically. In the case of toxicity, appropriate medical treatment should be used (including anti-emetics, anti-diarrheals, etc.).

All AEs experienced by participants will be collected from the time of the first dose of study treatment, through the study and until the final study visit. Participants continuing to experience toxicity at the off study visit may be contacted for additional assessments until the toxicity has resolved or is deemed irreversible.

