#### *Laboratory Abnormalities*

In the randomized clinical trial, Grade 1-4 neutropenia occurred in 15% of patients on enzalutamide (1% Grade 3-4) and in 6% of patients on placebo (no Grade 3-4). The incidence of Grade 1-4 thrombocytopenia was similar in both arms; 0.5% of patients on enzalutamide and 1% on placebo experienced Grade 3-4 thrombocytopenia. Grade 1-4 elevations in ALT occurred in 10% of patients on enzalutamide (0.3% Grade 3-4) and 18% of patients on placebo (0.5% Grade 3-4). Grade 1-4 elevations in bilirubin occurred in 3% of patients on enzalutamide and 2% of patients on placebo.

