**14.2 Analysis of Secondary Endpoints**

Safety and tolerability of enzalutamide will be evaluated. All participants who receive at least 1 dose of study drug will be included in these analyses. A summary of all Grade 1-4 treatment-related toxicities will be provided by toxicity type and maximum grade. The maximum grade consolidates the reports of a given type of toxicity for a participant over time by taking the maximum grade across time (i.e. a participant appears only once for a given type of toxicity). Participants with reports of multiple toxicities of different types are reported multiple times under the relevant toxicity categories. ‘Treatment-related’ toxicities are defined by an attribution as possible, probable or definite. With 66 participants, the maximum width of a 90% CI for a given toxicity rate is 22%. The probability of observing at least one rare severe toxicity (true rate=5%) is 95%. The number of cycles completed with and without dose modifications and treatment delays.

PSA response to enzalutamide will be summarized as frequency and percent. Participants who are unevaluable for response will be included in the denominator as nonresponders when calculating the response rate. Duration of PSA response for the regimen of enzalutamide will be defined relative to the first achievement of PSA response and will be estimated using the method of Kaplan and Meier. PSA response will be measured according to PCWG2 (2008) criteria.

Participants with measurable disease will be evaluated for response using RECIST 1.1 criteria. Duration of response of bone lesions or measurable disease will be described using Kaplan-Meier estimates.

The set of AR resistance measures will be summarized using descriptive statistics (mean, median, standard deviation (SD), interquartile range (IQR)). Correlation among measures will be assessed graphically with scatter plots and using Pearson correlation coefficients (or Spearman if appropriate).

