### **3.10 Safety Assessments and Toxicity Monitoring**

The study teams at all participating institutions are responsible for protecting the safety, rights and well-being of study participants. Recording and reporting of adverse events that occur during the course of a study help ensure the continuing safety of study participants.

All participants receiving investigational agents and/or other protocol mandated treatment will be evaluated for safety. The safety parameters include all laboratory tests and hematological abnormalities, physical examination findings, and spontaneous reports of adverse events reported by participants. All toxicities encountered during the study will be evaluated according to the NCI criteria specified in the protocol. Life-threatening toxicities must be reported immediately to the DF/HCC Sponsor via the Coordinating Center.

Additional safety assessments and toxicity monitoring will be outlined in the protocol.

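### The AE definition filters laboratory abnormalities by clinical consequence and is not reconciled with the grade-based safety text, so silent low-grade abnormalities can drop out of the section 14.2 summary

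*Combined protocol and SAP*

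**What the plan says.** Section 11.1.1 sets the rule for laboratory findings: "Abnormal laboratory values or diagnostic test results constitute AEs only if they induce clinical signs or symptoms or require treatment or further diagnostic tests". There are thus three routes to AE status: a clinical effect, a need for treatment, or a need for more testing.

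Other sections use grade or completeness and do not repeat the condition:

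- **Appendix E 3.10:** "The safety parameters include all laboratory tests and hematological abnormalities", followed by "All toxicities encountered during the study will be evaluated according to the NCI criteria specified in the protocol".
- **Sections 6 and 6.2:** action follows the CTCAE version 4 grade of an enzalutamide-related toxicity.
- **Section 6.1**, which section 11.1.3 names as the list of expected AEs: it reports neutropenia, thrombocytopenia, ALT and bilirubin by grade.
- **Section 14.2:** "A summary of all Grade 1-4 treatment-related toxicities will be provided by toxicity type and maximum grade".

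Section 9 schedules hematology, serum chemistry and liver function tests on day 1 of every cycle. No section plans a table of laboratory grades or says that grades will be derived from the values.

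**The concern.** Safety and tolerability is a secondary objective (section 1.3), and the 14.2 summary is its main output. If the toxicity CRF follows 11.1.1, a fall in neutrophils or a rise in ALT that causes no symptoms, is not treated and prompts no extra test has no place in that summary. Whether a value calls for further testing is a site decision, so two sites could record the same result differently.

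The rates that section 6.1.1 gives for enzalutamide are laboratory-graded, Grades 1 to 4. A rate from this trial that has passed through the 11.1.1 filter would not be comparable with them. Section 11.1.3 nevertheless uses frequency and intensity relative to the known list to decide whether an event is unexpected.

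**Working it through.** **1. The plan's own safety figures (section 14.2, 66 participants).**

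- Chance of at least one event at a true rate of 5%: 1 − 0.95^66 = 96.6%, against 95% stated.
- Maximum width of a 90% interval, at a rate of 50%: normal 2 × 1.645 × √(0.25/66) = 20.2%; exact (Clopper-Pearson) 21.4%; normal with continuity correction 20.2% + 1/66 = 21.8%. The stated figure is 22%.

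Both are reproduced closely enough. They take every event as captured.

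**2. Tracing a silent abnormality through the text.** Take a day-1 neutrophil count in the Grade 1 or 2 range with no symptoms, no treatment and no extra test.

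| Section | Treatment of that value |
|---|---|
| 11.1.1 | Not an AE |
| 11.1.4 | Attribution is defined only for AEs and SAEs |
| 11.2 | CTCAE grading is specified for AE reporting |
| 11.4.2 | Toxicity CRFs are the route for non-serious events |
| 12.1.2 | An AE form is scheduled; no on-treatment laboratory form is named |
| Appendix E 3.11.1 | Adverse events and toxicities are treated as the same thing |
| 14.2 | Related toxicities only, identified by attribution |

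The value has no stated route into the 14.2 summary. Yet Appendix E 3.10 names it as a safety parameter, and section 6.1 lists the abnormality among the expected events.

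**3. Expected numbers if the section 6.1.1 rates applied to 66 participants (66 × rate).**

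| Abnormality | Grade 1-4 | Grade 3-4 |
|---|---|---|
| Neutropenia | 15%: 9.9 | 1%: 0.66 |
| ALT elevation | 10%: 6.6 | 0.3%: 0.20 |
| Bilirubin elevation | 3%: 2.0 | not given |
| Thrombocytopenia | enzalutamide rate not given | 0.5%: 0.33 |

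By subtraction, Grade 1-2 accounts for about 9.2 of 9.9 neutropenia cases and 6.4 of 6.6 ALT cases. What the filter can remove is therefore nearly all low grade.

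**4. Sensitivity to capture.** The share of abnormalities that would meet 11.1.1 is not in the documents. For an assumed share c, the expected number recorded is 66 × rate × c. The chance of seeing at least one event at a true rate of 5% is 1 − (1 − 0.05c)^66.

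| c (assumed) | Neutropenia | ALT | Bilirubin | At least one, 5% rate |
|---|---|---|---|---|
| 100% | 9.9 | 6.6 | 2.0 | 96.6% |
| 75% | 7.4 | 5.0 | 1.5 | 92.0% |
| 50% | 5.0 | 3.3 | 1.0 | 81.2% |
| 25% | 2.5 | 1.7 | 0.5 | 56.4% |

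These are all-cause numbers, whereas 14.2 tabulates related events only. They show how the loss would scale and do not predict the 14.2 table.

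**5. The one in-document comparison of the two bases.** For the post-docetaxel randomized trial, section 2.1.1 gives liver-test abnormalities reported as AEs in 1% on enzalutamide and 2% on placebo. Section 6.1.1 gives laboratory-graded ALT elevation in 10% and 18%. The ratios are 10/1 = 10 and 18/2 = 9. For 66 participants that is 66 × 0.01 = 0.7 against 66 × 0.10 = 6.6. It appears to be the same trial (1,199 patients randomized 2:1 in one section; 800 + 399 = 1,199 in the other). The data cuts may differ, since seizures number 5 of 800 in section 2.1.1 and 7 of 800 in section 6.1.1. That trial's AE rule is not given. The comparison shows only that the two bases can differ widely for this drug.

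**The case against.** The strongest reply is that a clinical-relevance filter is a deliberate choice, that safety is secondary here, and that enzalutamide is an approved drug in an IND-exempt study. The CRFs are not in the documents and might hold all graded values. The per-cycle results exist in any case, so nothing is irrecoverable. This stands as far as it goes: the omission is a risk, not a certainty. It does not answer the missing route in step 2 of the working.

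Four stronger readings are tempting, and the documents do not support them.

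- **Most laboratory toxicity will be lost.** A reader might set an assumed silent share against the 15% and 10% rates. Those rates are all-cause, the share is unknown, and 14.2 is limited to related events. ALT elevation was less frequent on enzalutamide (10%) than on placebo (18%), so attribution alone could remove many cases.
- **A silent Grade 3 value goes ungraded and unattributed.** Section 6 acts on enzalutamide-related toxicity above Grade 2, so such a value must already be graded and attributed. Showing that it has resolved needs re-testing, which would often meet the third route of 11.1.1, although a re-test could fall at a scheduled visit.
- **The DSMC could not see laboratory trends.** Section 12.2 lets it have laboratory values on request. What stands is that they are not routine. The AE item listed there is limited to unexpected events of Grade 2 or higher, and these abnormalities are on the expected list. Rewording 11.1.1 alone would therefore not bring most of them to the committee.
- **Appendix E 3.10 makes every laboratory abnormality an AE.** It names them as safety parameters to be evaluated, which is less than that.

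**Conclusion.** The point holds as an unreconciled definition with a foreseeable effect on a secondary endpoint. As written, silent abnormalities, mainly Grade 1-2 neutropenia and ALT elevation, can be absent from the 14.2 summary, and capture can vary by site. The size cannot be computed from the documents. The tenfold gap in step 5 is an illustration, and the capture table rests on assumed shares of 25% to 75% and on the earlier trial's rates carrying over to 66 participants. Grade 3-4 laboratory events are expected to be few, about 0.2 to 0.7 per type, so the effect there is small. The precision figures in 14.2 are not in error. The change should be made because it is cheap and resolves a real inconsistency.

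**What to change.** - In section 14.2, add a laboratory table giving worst on-treatment CTCAE version 4 grade and shift from baseline. Derive it from the hematology, chemistry and liver results already drawn on day 1 of each cycle. Report it separately from the treatment-related AE table, so that neither symptoms nor attribution decides what appears.
- Include this table in the summary that the study team gives the DSMC.
- Define toxicity in relation to AE, and state whether graded values that fail 11.1.1 go on the toxicity CRF.
- Reconcile 11.1.1 with sections 6 and 6.2 and Appendix E 3.10. This concerns what is recorded; no dosing rule needs to change.

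The cost is some programming, CRF capture of laboratory values if they are not already collected, and a display with more low-grade abnormalities. No new tests are needed.

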#### 11.1.2 Serious adverse event (SAE)

A SAE is any adverse event, occurring at any dose and regardless of causality that:

- Results in death
- Is life-threatening. Life-threatening means that the person was at immediate risk of death from the reaction as it occurred, i.e., it does not include a reaction which hypothetically might have caused death had it occurred in a more severe form.
- Requires or prolongs inpatient hospitalization (i.e., the event required at least a 24-hour hospitalization or prolonged a hospitalization beyond the expected length of stay). Hospitalization admissions and/or surgical operations scheduled to occur during the study period, but planned prior to study entry are not considered SAEs if the illness or disease existed before the person was enrolled in the trial, provided that it did not deteriorate in an unexpected manner during the trial (e.g., surgery performed earlier than planned).
- Results in persistent or significant disability/incapacity. Disability is defined as a substantial disruption of a person's ability to conduct normal life functions.
- Is a congenital anomaly or birth defect; or
- Is an important medical event when, based upon appropriate medical judgment, it may jeopardize the participant and require medical or surgical intervention to prevent one of the outcomes listed above. Examples of such medical events include allergic bronchospasm requiring intensive treatment in an emergency room or at home; blood dyscrasias or convulsions that do not result in inpatient hospitalization, or the development of drug dependency or drug abuse.

Events **not** considered to be SAEs are hospitalizations for:

CONFIDENTIAL

This document is confidential. Do not disclose or use except as authorized.

- routine treatment or monitoring of the studied indication, not associated with any deterioration in condition, or for elective procedures
- elective or pre-planned treatment for a pre-existing condition that did not worsen
- emergency outpatient treatment for an event not fulfilling the serious criteria outlined above and not resulting in inpatient admission
- respite care

### 11.1.3 Expectedness

AEs can be 'Expected' or 'Unexpected.'

- Expected AE

Expected AEs are those that have been previously identified as resulting from administration of the agent. For the purposes of this study, an AE is considered expected when it appears in the current AE list, the Investigator's Brochure, the package insert or is included in the informed consent document as a potential risk.

Refer to Section 6.1 for a listing of expected AEs associated with the study agent(s).

- Unexpected AE

For the purposes of this study, an AE is considered unexpected when it varies in nature, intensity or frequency from information provided in the current AE list, the Investigator's Brochure, the package insert or when it is not included in the informed consent document as a potential risk.

### 11.1.4 Attribution

Attribution is the relationship between an AE or SAE and the study treatment. Attribution will be assigned as follows:

- Definite – The AE is clearly related to the study treatment.
- Probable – The AE is likely related to the study treatment.
- Possible – The AE may be related to the study treatment.
- Unlikely - The AE is doubtfully related to the study treatment.
- Unrelated - The AE is clearly NOT related to the study treatment.

## 11.2 Procedures for AE and SAE Recording and Reporting

CONFIDENTIAL

This document is confidential. Do not disclose or use except as authorized.

Participating investigators will assess the occurrence of AEs and SAEs at all participant evaluation time points during the study.

All AEs and SAEs whether reported by the participant, discovered during questioning, directly observed, or detected by physical examination, laboratory test or other means, will be recorded in the participant's medical record and on the appropriate study-specific case report forms.

The descriptions and grading scales found in the revised NCI CTCAE version 4.0 will be utilized for AE reporting. All appropriate treatment areas should have access to a copy of the CTCAE version 4.0.

A copy of the CTCAE version 4.0 can be downloaded from the CTEP website at: [http://ctep.cancer.gov/protocolDevelopment/electronic\\_applications/ctc.htm](http://ctep.cancer.gov/protocolDevelopment/electronic_applications/ctc.htm).

### **11.3 Reporting Requirements**

The DF/HCC will serve as the coordinating center for this multi-site trial. Each participating investigator is required to abide by the reporting requirements set by the DF/HCC. The study must be conducted in compliance with FDA regulations, local safety reporting requirements, and reporting requirements of the principal investigator. Each investigative site will be responsible to report SAEs that occur at that institution to their respective IRB. It is the responsibility of each participating investigator to report SAEs to the study sponsor and/or others as described below.

### **11.4 Reporting to the Study Sponsor**

#### **11.4.1 SAE Reporting**

All SAEs that occur after the initial dose of study treatment, during treatment, or within 30 days of the last dose of treatment must be reported to the DF/HCC Overall PI on the local institutional SAE form. This includes events meeting the criteria outlined in Section 11.1.2, as well as the following:

- Grade 2 (moderate) and Grade 3 (severe) Events – Only events that are unexpected and possibly, probably or definitely related/associated with the intervention.
- All Grade 4 (life-threatening or disabling) Events – Unless expected AND specifically listed in the protocol as not requiring reporting.
- All Grade 5 (fatal) Events – When the participant is enrolled and actively participating in the trial OR when the event occurs within 30 days of the last study intervention.

CONFIDENTIAL

This document is confidential. Do not disclose or use except as authorized.

Note: If the participant is in long term follow up, report the death at the time of continuing review.

Participating investigators must report each SAE to the DF/HCC Overall PI and Astellas Pharmaco-Vigilance Department within 24 hours of learning of the occurrence. In the event that the participating investigator does not become aware of the SAE immediately (e.g., participant sought treatment elsewhere), the participating investigator is to report the event within 24 hours after learning of it and document the time of his or her first awareness of the AE. Report SAEs by telephone, email or facsimile to:

[REDACTED]  
[REDACTED]  
[REDACTED]  
[REDACTED]

Astellas Pharma Global Department – United States

[REDACTED]  
[REDACTED]

Within the following 24-48 hours, the participating investigator must provide follow-up information on the SAE. Follow-up information should describe whether the event has resolved or continues, if and how the event was treated, and whether the participant will continue or discontinue study participation.

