## **4. REGISTRATION PROCEDURES**

### **4.1 General Guidelines for DF/HCC and DF/PCC Institutions**

Institutions will register eligible participants in the Clinical Trials Management System (CTMS) OnCore. Registrations must occur prior to the initiation of protocol therapy. Any participant not registered to the protocol before protocol therapy begins will be considered ineligible and registration will be denied.

An investigator will confirm eligibility criteria and a member of the study team will complete the protocol-specific eligibility checklist.

Following registration, participants may begin protocol therapy. Issues that would cause treatment delays should be discussed with the Overall Principal Investigator (PI). If a participant does not receive protocol therapy following registration, the participant's registration on the study must be canceled. Registration cancellations must be made in OnCore as soon as possible.

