## 5. TREATMENT PLAN

All protocol required therapy will be prescribed by prescription and taken by the participant on an outpatient basis. A baseline metastasis biopsy will be done prior to starting protocol therapy.

Participants will be treated with four 40 mg capsules (160 mg) once daily of enzalutamide taken orally. All participants without orchiectomy will be maintained on LHRH agonist/antagonist therapy. Participants will be evaluated clinically and with laboratory studies on day 1 of every 28 day cycle. Participants will maintain a drug diary from time of initiation of study treatment to time of discontinuation from the study (Appendix C). Participants will be continued on therapy until evidence of symptomatic or radiographic progression or taken off study for another reason.

A metastasis biopsy will be performed while the participant is still on enzalutamide at the time of progression. For DFCI participants, if the biopsy site (baseline and progression) is a pelvic bone both an aspirate and core biopsy will be obtained. After progression biopsy is performed, protocol therapy will be discontinued. Participants who stop protocol therapy before receiving four cycles of enzalutamide will not be asked to undergo a second biopsy. The tumor biopsy at the end of study is otherwise mandatory and can be done +/- 14 days of determination of progression. Situation where the participant stops protocol therapy for reasons other than progression after receiving 4 cycles of enzalutamide should be discussed with the PI if it is felt that biopsy would not represent progressive disease. For DFCI participants, quantitative SPECT/CT imaging substudy will be performed in addition to standard bone scanning at baseline and at the time of the first two follow up bone scans.

Expected toxicities and potential risks as well as dose modifications for enzalutamide are described in Section 6 (Expected Toxicities and Dosing Delays/Dose Modifications). No investigational or commercial agents or therapies other than those described below may be administered with the intent to treat the participant's malignancy.

Treatment Description					
Agent	Pre-medications; Precautions	Dose	Route	Schedule	Cycle Length
Enzalutamide	Can be taken with or without food. The capsules should be swallowed whole with water. Do not chew, dissolve, or open capsules.	160 mg	Oral	Once daily	28 days (4 weeks)

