- l: For DFCI participants only, one bed position of quantitative SPECT/CT will be performed as an imaging substudy concurrently with the standard of care bone scans at baseline and at the time of the first two follow up standard of care bone scans. The field of view will be determined by the nuclear medicine physician depending on the location of the lesions on the planar images.
- m: Study agent is enzalutamide. Subjects will be continued on LHRH agonist/antagonist as prescribed. Subjects will begin taking study agent on Day 1/Cycle 1.
- n: AEs should be collected from the date informed consent is signed until 30 days after discontinuation from the study.
- o: Tumor biopsy must be performed prior to starting study medication. Participants will need to be screening and registered before having a biopsy. Friday should be avoided due to difficult of processing bone biopsies on the weekend. For DFCI participants, if the biopsy site (baseline and progression) is a pelvic bone both an aspirate and core biopsy will be obtained.
- p: Participants who stop the protocol therapy before receiving four cycles of enzalutamide will not be asked to undergo the second biopsy. The tumor biopsy at the end of the study can be done +/- 14 days of the determination of progression. Enzalutamide will be discontinued following completion of the second biopsy. Situations where the participant stops protocol therapy for reasons other than progression after receiving four cycles of enzalutamide should be discussed with the PI if it felt that the biopsy would not represent progressive disease.
- q: The End of Treatment Visit will be the visit at which it is determined that the patient will no longer be taking treatment given disease progression, toxicity, or other reason.
- r: Follow up Visits: Participants will be followed for up to 5 years post-study discontinuation or until death, whichever comes first. Participant follow up visits will be at the research clinic for the first 2 years of follow-up. Following the first 2 years, participant follow-up can be done via medical record review and/or by phone. Participants will be followed for subsequent lines of therapy, including line of agent, name of agent, and PSA kinetics following study drug discontinuation and correlate with response to study drug. This information will be updated every 6 months. The research team will collect this information during patient clinic visits, by phone, or via medical record review.

CONFIDENTIAL

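### AE collection starts at first dose in section 6 but at consent in the study calendar, so cover for a non-fatal SAE from the pre-dose biopsy is unclear; separately, the 14.2 toxicity summary stops at Grade 4

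*Combined protocol and SAP*

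**What the plan says.** On the start of collection, section 6 states: "All AEs experienced by participants will be collected from the time of the first dose of study treatment". Note n to the study calendar (section 9) states: "AEs should be collected from the date informed consent is signed until 30 days after discontinuation from the study". The calendar itself marks adverse events in the Pre-Study column. The definition in section 11.1.1 covers an event that "develops or worsens in severity after starting the first dose of study treatment or any procedure specified in the protocol".

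On SAE reports to the Overall PI, section 11.4.1 opens with "All SAEs that occur after the initial dose of study treatment" and then extends the window through treatment to 30 days after the last dose. Later in the same section comes "Participating investigators must report each SAE to the DF/HCC Overall PI", with a 24-hour limit from awareness and no statement of when the duty begins.

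On the order of events, section 5 says: "A baseline metastasis biopsy will be done prior to starting protocol therapy". Note o adds: "Participants will need to be screening and registered before having a biopsy". The biopsy therefore lies between registration and first dose.

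On analysis, section 14.2 takes everyone with at least one dose and summarizes treatment-related toxicities of Grades 1 to 4 by type and maximum grade.

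**The concern.** A site cannot follow both section 6 and note n for the time before dosing, and that time contains an invasive procedure planned for all 66 participants. Two sites acting in good faith could handle the same biopsy complication differently: one records it, the other does not. On reporting, the opening of 11.4.1 and its 24-hour sentence allow two defensible readings of the same duty. What is at stake is uniform capture and timely sponsor knowledge of procedure-related harm.

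The Grade 5 point concerns the planned summary. Safety and tolerability is a secondary objective (section 1.3), and the planned toxicity table has no place for its most severe grade.

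**Working it through.** **1. Start points side by side**

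| Place | Function | Start |
|---|---|---|
| Section 6 | AE collection | First dose |
| Section 9, note n and Pre-Study mark | AE collection | Signed consent |
| Section 11.1.1 | AE definition | First dose or any protocol procedure |
| Section 11.4.1, opening | SAE report to Overall PI | After initial dose |
| Section 11.4.1, 24-hour sentence | SAE report to Overall PI | None stated |
| Section 11.2 | Recording of AEs and SAEs | None stated |
| Section 11.8 | Follow-up of events | Start of study intervention, a term not defined |

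Two passages set a start for collection, and they differ.

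**2. One event traced through the rules**

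Suppose a registered participant is hospitalized for more than 24 hours after the baseline biopsy, before any drug, with a complication that is neither fatal nor life-threatening.

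- Sections 11.1.1 and 11.1.2: it is an AE, because it follows a protocol procedure, and it is serious because of the hospitalization.
- Section 6: outside collection. Note n: inside collection.
- Section 11.4.1: outside on the opening sentence; inside if the 24-hour sentence is read on its own.
- Section 5.6 and Appendix E 3.10: immediate notice covers unusual or life-threatening complications and life-threatening toxicities, so this event need not qualify.

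The interval at issue runs from biopsy to first dose. Section 4.3 asks outside sites to start treatment within 5 days of registration. Section 4.1 gives DF/HCC sites no limit.

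**3. Scale**

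The plan's own figure comes first. Section 14.2 gives a 95% chance of seeing at least one toxicity with a true rate of 5% in 66 participants. The formula 1 − (1 − p)^66 gives 1 − 0.95^66 = 96.6%, which agrees to within 2 points.

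The same formula with n = 66 and an assumed biopsy SAE rate p (none is given in the documents):

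| Assumed p | Expected, 66p | Chance of at least one |
|---|---|---|
| 0.5% | 0.33 | 28.2% |
| 1% | 0.66 | 48.5% |
| 2% | 1.32 | 73.6% |

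These count every biopsy SAE. The exposed ones are only those that occur before dosing, are non-fatal and fall outside the immediate-notice rules; non-collection further requires a site that follows section 6 rather than note n. The figures are therefore upper illustrations at each assumed rate.

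**4. Grade 5**

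Section 11.4.1 treats Grade 5 as fatal, so 14.2 tabulates 4 of 5 grades. With the maximum taken over Grades 1 to 4, a fatal related toxicity is absent if no lower grade was recorded earlier, and otherwise appears at that lower grade.

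For scale, section 2.1.1 reports no deaths in the phase I/II trial. Section 6.1.1 reports deaths from infection or sepsis of 1.0% versus 0.3% in the randomized trial, without attribution. If the related-death rate is assumed to lie between 0 and 1.0%, the expected count in 66 is 0 to 0.66 and the chance of at least one is 0 to 48.5%. At the difference of 0.7%, these are 0.46 and 37.1%. This is a range for illustration, not an estimate of related deaths.

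**The case against.** The strongest reply is that section 11 already covers the biopsy event. Its definition includes protocol procedures, section 11.2 requires all AEs and SAEs to be recorded on case report forms, and Appendix E 3.10.1 names section 11 as the place for the reporting rules. Against this stands one sentence in the dose-modification section. SAEs also go to the IRBs (sections 11.3 and 11.5) and, from outside sites, through the Coordinating Center to the sponsor for timely review (Appendix E 2.2). Appendix E 3.10.1 also points to DFCI IRB reporting requirements, which are not in the documents and may set a start and a time limit. All of this narrows the gap. It does not close it: 11.2 gives no start date, section 6 is current text, and the visible wording leaves the two starts unreconciled. It is also fair that collecting AEs from consent while opening sponsor SAE reports at first dose would not by itself be a contradiction. The difficulty is that 11.4.1 is unclear about its own start.

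Some stronger readings are tempting but not supported:

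- *A pre-dose SAE carries no reporting deadline.* The 24-hour sentence can be read to cover it, and life-threatening events call for immediate notice.
- *Deaths would escape notice.* The Grade 5 item in 11.4.1 turns on being enrolled and active, not on dosing, and section 12.2 allows deaths to be shown to the DSMC. The Grade 5 omission concerns the 14.2 summary alone.
- *An event that prevents dosing is erased.* Section 4.1 says the "registration on the study must be canceled" when no therapy is given, but nothing says that records are discarded, and sections 13.4 and 13.5 require complete case histories and retention. A sentence on this would add detail; its absence is not an error.
- *The 14.2 table would change with the start date.* It would not: the table is limited to dosed participants and treatment-related toxicity.

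**Conclusion.** The point holds as an inconsistency in safety capture and reporting, with a separate omission in the safety summary. Sections 6 and 9 contradict each other on when AE collection starts, and 11.4.1 is ambiguous on whether a non-fatal pre-dose SAE falls under the 24-hour report. Both matter because every participant is to have a biopsy in the disputed interval. The number of events affected cannot be estimated from the documents. The 28% to 74% range rests on assumed rates of 0.5% to 2% for all biopsy SAEs in 66 participants; a reader might take it as the chance of an unreported SAE, which it is not. The Grade 5 omission matters only if a related death occurs, but the planned summary would then be wrong at its most serious entry. Sample size, power and the primary biopsy-marker analysis do not depend on either point. The correction should be made: the benefit is modest and the cost is small.

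**What to change.** Reconcile section 6 and the opening of 11.4.1 with note n, so that AE collection and SAE reporting share one start point that covers the baseline biopsy. Signed consent, already in note n, does this. State in 11.4.1 that the 24-hour sentence runs from that point. In 14.2, change the summary to Grades 1 to 5.

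The cost is protocol wording and perhaps a few additional pre-dose SAE reports. Section 12.1.2 ties the AE form to the end of a cycle, so sites should also be told when to submit an event that precedes cycle 1. The form itself is not in the documents, so whether it needs a change cannot be judged here.
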